## 2.2 BACKGROUND

ALS is a fatal neurodegenerative disorder characterized by progressive loss of motor neurons in the cortex, brain stem, and spinal cord. Relentless and progressive muscle atrophy and weakness are hallmarks of ALS. Most patients with ALS die from respiratory failure within 3 to 5 years after disease onset. Among the 3 Food and Drug Administration (FDA)-approved ALS treatments, riluzole and edaravone demonstrate only a moderate effect either on survival or functional decline, respectively, and more data is needed to further support the treatment effect of the recently approved treatment, the combination of sodium phenylbutyrate and taurursodiol. Therefore, there is still a significant unmet medical need for treating individuals with ALS.

SAR443820 has demonstrated strong RIPK1 inhibition with high potency in vitro in various cell types. Refer to the SAR443820 Investigator's Brochure (IB) for a detailed description of the chemistry, pharmacology, efficacy, and safety of SAR443820.

## 2.3 BENEFIT/RISK ASSESSMENT

### 2.3.1 Risk assessment

**Table 1 - Risk assessment (identified risk of clinical significance)**

Identified risk of clinical significance	Summary of data/rationale for risk	Mitigation strategy
Study intervention(s)		
ALT increase/Drug induced liver injury (DILI)	During clinical trials with SAR443820, mild-severe ALT increases have been reported, including 2 SUSARs with total bilirubin increase $> 2$ ULN reported in the ALS patients. These events often involved patients who were also taking concomitant medications that are known to induce liver function abnormalities, or who had concomitant diseases that could also affect ALT level.	Implemented through an USM dated on 5th December 2023, all participants in Part A are requested to conduct weekly liver chemistry monitoring and all participants in Part B are requested to pause SAR443820 immediately until DMC recommendation to resume dosing based on benefit-risk considerations when Part A data is available. Additionally, all participants are requested to limit their alcohol consumption during the whole study period.  Detailed instructions to be followed in case of the occurrence of an AESI of ALT increase $> 3$ ULN are described in Appendix 6 in this protocol, and cover ALT monitoring, IMP administration, etiology assessment and IMP rechallenge.

Abbreviations: ALT=alanine transaminase; DILI=drug induced liver injury; IMP=investigational medicinal product, SUSAR=suspected unexpected serious adverse event, ULN=upper limit normal, USM=urgent safety measure, AESI=adverse event of special interest

**Table 2 - Risk assessment (potential risk of clinical significance)**

Potential risk of clinical significance	Summary of data/rationale for risk	Mitigation strategy
Study intervention(s)		
Convulsion	
Convulsions are considered to be a potential risk based on nonclinical findings in single-dose, 9-day and 28-day nonhuman primate toxicity studies and in a 6-month rat study.
 
In nonhuman primate studies, the following were observed: Convulsions/tremors at a dose of 75 mg/kg in the single-dose study, at a dose of 100 mg/kg/day in the 9-day study, and at a dose of 60 mg/kg/day in the 28-day study.
 
No convulsions have been observed up to the dose level of [REDACTED] mg/kg/day in both the 3-month and 9-month studies.
 
In the 6-month study in rats, convulsions were noted at a dose of 400 mg/kg/day (males) and 200 mg/kg/day (females). Convulsions and other findings that necessitated euthanasia were also observed in a single female rat receiving 50 mg/kg/day.
	
Based on the uncertainty in the interspecies translatability of convulsive risk, a conservative safety approach to limit human exposure (ie, <math>C_{max}</math> and AUC) was taken regarding the selected dose of 20 mg BID, which maintained a [REDACTED] to the NOAEL exposure (<math>C_{max}</math> and AUC) in the 3-month toxicology study in nonhuman primates.
 
Moreover, to mitigate the risk, participants with a history of seizure will not be eligible to participate in this study.
 
Additionally, concomitant medications that may increase significantly exposure [REDACTED] (including strong and moderate CYP3A4 inhibitors) are not allowed in this study. Patients in whom exposure may be [REDACTED] (participants weighing <45 kg or patients with a moderate or severe hepatic impairment) will also be excluded from this study.

Immunomodulatory Effects	
Findings consistent with immune system modulation were observed with SAR443820 in the 3-month and 9-month nonhuman primate studies. These findings included mononuclear cell infiltrates in various tissues and changes in lymphoid tissues (increased/decreased cellularity and/or increased germinal centers).
 
None of these microscopic findings for SAR443820 were considered adverse based on their incidence, severity, and/or recoverability or the lack of clinical pathology correlates or relevant clinical observations.
	
Frequent monitoring of the results of a hematology test, physical examinations (eg, skin, lymph nodes), and occurrence of infections TEAEs are planned.

Pregnancy maintenance and embryo-fetal toxicity	
Adverse, test article-related effects on litter viability/pregnancy maintenance were noted at 200 mg/kg/day in a rat embryo-fetal development study. Two rats given 200 mg/kg/day were pregnant but had total litter loss. In addition, test article-related increases in early resorptions, late resorptions, total resorptions, post implantation loss, post-implantation loss percentage, and reduced fetal weight were observed for groups administered 20, 60, or 200 mg/kg/day.
	
Pregnant females are not allowed to participate in this study and monthly pregnancy testing is requested for all female participants of childbearing potential. Pregnancy of a female participant will lead to permanent IMP discontinuation in the participant. Additionally, contraceptive use by female participants of childbearing potential is requested during study period.

Study procedures		
Blood drawing	Pain or other discomfort from collection of blood samples.	Minimize the frequency and amount of blood drawing.

Abbreviations: AESI = adverse event of special interest; ALT = alanine transaminase; AUC = area under the curve; BID = twice daily;  $C_{max}$  = maximum plasma concentration; CYP = cytochrome P450; IMP = investigational medicinal product; NOAEL = no-observed-adverse-effect level; TEAEs = treatment-emergent adverse events. ULN = upper limit of normal.

### **2.3.2 Benefit assessment**

SAR443820 is expected to slow disease progression, improve quality of life (QoL), and prolong survival for participants with ALS based on scientific rationale and preclinical data.

### **2.3.3 Overall benefit/risk conclusion**

In the completed first-in-human studies, SAR443820 was found to be safe and well-tolerated up to the highest doses administered, ie, a single dose of [REDACTED] mg and multiple 14-day dose of 20 mg BID, in 100 healthy subjects who received SAR443820 as of April 2022. In addition, a preliminary physiological based pharmacokinetic modeling and simulation (PBPK) model indicates that at a dose of 20 mg SAR443820 BID, [REDACTED]

[figure not shown]
[REDACTED] value determined in vivo using the pS166-RIPK1 inhibitor assay in peripheral blood mononuclear cells (PBMC), which supports the potential for clinical efficacy. Convulsions believed to be SAR443820-related have been observed in [REDACTED]. The risk of convulsions will be mitigated through 1) limiting the dose chosen in this study with maximum plasma concentration ( $C_{max}$ ) and area under the curve (AUC) [REDACTED] at the no-observed-adverse-effect-level (NOAEL) in the 3-month monkey study; 2) excluding participants with a history of seizures; 3) excluding concomitant medications that may increase exposure [REDACTED] (potent and moderate cytochrome P450 (CYP)3A4 inhibitors); and 4) excluding participants with moderate or severe hepatic impairment. Since immunomodulatory effects of SAR443820 were observed in the 3-month nonhuman primate study but not in the first-in-human study in healthy volunteers, frequent monitoring of safety through hematology tests, physical examinations (eg, skin, lymph nodes), and the occurrence of infection, will be implemented in both Parts A and B. Considering the measures taken to minimize risk to participants in this study, the potential risks identified in association with SAR443820 are justified by the anticipated benefits that may be afforded to participants with ALS.

In the ongoing study ACT16970, a limited number of cases meeting criteria for severe DILI have been reported. ALT and bilirubin levels fully recovered in these cases after stopping the IMP and riluzole. These blinded data suggest that DILI is an identified risk of SAR443820, in particular when used in combination with hepatotoxic concomitant medications. The exact mechanism is not known. In nonclinical studies in rats and monkeys, non-adverse microscopic changes were noted in the liver without ALT increases. In Phase 1 studies, there were three mild (<3 ULN) asymptomatic cases of ALT increase (all recovered). Risk minimization measures during the study include limitation of alcohol consumption, although a relationship with alcohol use has not been established. In addition, frequent monitoring of liver chemistry is implemented to allow for early detection and mitigation. The Benefit Risk ratio remains acceptable for the use of SAR443820 in participants with ALS.

[figure not shown]
### 3 OBJECTIVES AND ENDPOINTS

**Table 3 - Objectives and endpoints**

#### Part A

	Objectives	Endpoints
Primary	

To assess the effect of SAR443820 compared to placebo in reducing ALS progression as measured by the Amyotrophic Lateral Sclerosis Functional Rating Scale Revised (ALSFRS-R)

	

Change from baseline in the ALSFRS-R total score to Week 24

Secondary	

To assess the effect of SAR443820 compared to placebo on a combined assessment of function and survival, respiratory function, muscle strength, and quality of life (QoL)

To assess the pharmacodynamic (PD) effect of SAR443820 compared to placebo on a key disease biomarker

To assess the safety and tolerability of SAR443820 compared to placebo

To assess the pharmacokinetics (PK) of SAR443820

	

Combined assessment of the function and survival (CAFS) score at Week 24

Change from baseline in slow vital capacity (SVC) to Week 24

Change from baseline in muscle strength to Week 24

Change from baseline in Amyotrophic Lateral Sclerosis Assessment Questionnaire (ALSAQ-5) to Week 24

Change from baseline in serum neurofilament light chain (NfL) to Week 24

Incidence of adverse events (AE), serious adverse events (SAE), treatment-emergent adverse events (TEAE), potentially clinically significant abnormalities (PCSA) in laboratory tests, electrocardiogram (ECG), and vital signs over 24 weeks

Plasma concentration of SAR443820

Tertiary	
SAR443820
  

To assess the effects of SAR443820 compared to placebo on neurodegeneration and inflammation disease biomarkers

	 

Change from baseline in soluble triggering receptor expressed on myeloid cells-2 (sTREM2) in plasma chitinase-3-like protein-1 (CHI3L1), a selected panel of cytokines and chemokines in serum, and extracellular domain of p75 (p75ECD) in urine to Week 24

## Part B

	Objectives	Endpoints
Primary		
	

• To assess the long-term effects of SAR443820 on function and survival

	

• Combined assessment of the function and survival (CAFS) score at Week 52

Secondary	

• To assess the long-term effects of SAR443820 on disease progression, survival, respiratory function, and quality of life (QoL)

	

• Combined assessment of the function and survival (CAFS) score at Week 76 and Week 104

• Change from baseline in the ALSFRS-R total score to Week 52, Week 76, and Week 104

• Time from baseline to the occurrence of either death or permanent assisted ventilation (>22 hours daily for >7 consecutive days), whichever comes first

• Time from baseline to the occurrence of death

• Change from baseline in slow vital capacity (SVC) to Week 52, Week 76, and Week 104

• Change from baseline in Amyotrophic Lateral Sclerosis Assessment Questionnaire (ALSAQ-5) to Week 52, Week 76, and Week 104

• Change from baseline in serum neurofilament light chain (NfL) to Week 52

• Incidence of adverse events (AE), serious adverse events (SAE), treatment-emergent adverse events (TEAE), potentially clinically significant abnormalities (PCSA) in laboratory tests, electrocardiogram (ECG), and vital signs during Part B

• Plasma concentration of SAR443820

Tertiary	
SAR443820
  
SAR443820
 	           

For China, please see Appendix 8 ([Section 10.8](#)) for details.

### **3.1 APPROPRIATENESS OF MEASUREMENTS**

#### **3.1.1 Measurements for efficacy assessment**

The primary endpoint of this study is the change of ALS disease progression as measured by the ALSFRS-R, which is a validated and established outcome measurement of therapeutic efficacy for ALS. The ALSFRS-R is a widely accepted measure of ALS progression used by clinical trialists and regulatory bodies (14).

[figure not shown]
The CAFS is a measurement ranking the clinical outcomes of patients with ALS based on survival time and change in the ALSFRS-R score (15). The combined endpoint can decrease the confounding effect of mortality on the results of an analysis of functional outcomes as it appropriately accounts for and weights mortality in the analysis of function.

For the survival assessment, in addition to mortality, a composite time-to-event endpoint recording the time to death or permanent continuous ventilator dependence, whichever occurs first, will be assessed as 1 of the efficacy endpoints since survival data may be confounded by the use of ventilation strategies. This approach is consistent with guidance from the FDA and European Medicines Agency (EMA) (14, 16).

The SVC percentage of predicted normal provides a quantitative means to assess reductions in the strength of the diaphragm and other respiratory muscles. The SVC change over time has been demonstrated to be associated with meaningful clinical events, including the time to respiratory insufficiency or death (17).

Muscle weakness is a typical feature of ALS and an important determinant of participants' daily function and QoL. Handheld dynamometry provides a quantitative means to assess limb muscle strength.

The ALSAQ-5 has been demonstrated to be a sensitive and reliable instrument for estimating QoL in patients with ALS (18) and provides similar results to the ALSAQ-40 but with a considerable reduction in patient burden (19).

.....

#### **3.1.2 Pharmacokinetic assessments**

Whole blood samples will be collected for measurement of the plasma concentration of SAR443820 as specified in the schedule of assessments (SoA).

### **3.1.3 Pharmacodynamic assessments**

Serum blood samples will be used to measure changes in NfL, a marker of neuronal injury. Levels of NfL in both CSF and plasma have been reported to be increased and stable over time in participant with ALS compared to healthy controls. Patients with ALS with a fast progression rate have demonstrated higher levels of NfL in CSF and plasma than those with a slow progression rate (21). Only serum NfL will be measured in this study to reduce the collection burden on participants.

Blood samples will also be collected to measure changes in markers of neuroinflammation, including soluble triggering receptor expressed on myeloid cells 2 (sTREM2) in plasma, Chitinase-3-like protein 1 (CHI3L1), and several cytokines in serum (interferon gamma [IFN $\gamma$ ], interleukin [IL]-1 $\beta$ , IL-2, IL-4, IL-6, IL-8, IL-10, IL12p70, IL-13, and TNF- $\alpha$ ) and chemokines (eotaxin 1, eotaxin 3, thymus- and activation-regulated chemokine [TARC], interferon gamma-induced protein-10 [IP-10], macrophage inflammatory protein (MIP) (MIP1 $\alpha$  and MIP1 $\beta$ ), monocyte chemoattractant proteins (MCP) 1 and 4 (MCP1 and MCP4).

Urine samples will be collected to measure changes in the level of neurotrophin receptor extracellular domain p75 (p75ECD).

### **3.1.4 Safety and tolerability assessment**

Adverse events (AE), serious adverse events (SAE), treatment-emergent adverse events (TEAE), adverse events of special interest (AESI), electrocardiogram (ECG), vital signs, and laboratory test analyses will be reported.

## 4 STUDY DESIGN

### 4.1 OVERALL DESIGN

Study ACT16970 is a Phase 2, randomized, double-blind, placebo-controlled, 2 parallel-group study followed by an open-label, long-term extension period.

The study consists of 2 parts (A and B) as follows:

**Part A** is a 24-week, double-blind, placebo-controlled part, preceded by a screening period of up to 4 weeks before Day 1.

- A screening period of up to 4 weeks, designed to evaluate the suitability of participants to participate in the study in terms of ALS diagnosis, ALS duration, and ALS progression rate; respiratory function (SVC); and safety screening evaluations. No IMP will be administered in this period.
- A double-blind treatment period with a total duration of 24 weeks for each participant:
  - Participants will be randomized in a ratio of 2:1 to receive 20 mg BID SAR443820 (n=174) or placebo BID (n=87).
  - Randomization will be stratified by the geographic region of the study site, region of ALS onset (bulbar vs other areas), use of riluzole (yes vs no), and use of edaravone (yes vs no) and use of the combination of sodium phenylbutyrate and taurursodiol (yes vs no). Participants will attend in-clinic study assessments at baseline (Day 1), Week 2, Week 4, Week 6, Week 8, Week 10, Week 12, Week 16, Week 20, Week 21, Week 22, Week 23, and Week 24. All ongoing participants at Week 24 will rollover to open-label extension (Part B).
- Participants who discontinue the treatment or choose not to enter Part B will have their follow-up visit 2 weeks after the last dose of the study intervention.

**Part B** is an open-label, long-term extension of Part A. Part B starts from Week 24 and continues up to Week 106.

- The study intervention assignment of participants in Part A will remain double-blinded during Part B unless there is medical need to unblind the study intervention assignment.
- All participants will receive 20 mg BID SAR443820 in Part B starting from Week 24, except those who discontinue IMP treatment permanently in Part A.

Based on a data review, and in accordance with Data Monitoring Committee (DMC) recommendations, sites have been instructed on 5th December 2023 to pause the administration of SAR443820 in Part B (open-label extension) immediately. All participants in Part B will be encouraged to continue follow-up visits, but no doses of SAR443820 should be administered. Rollover to Part B for follow-up visits after completing Part A is also encouraged, but without taking SAR443820 in Part B. The decision of whether resuming SAR443820 administration in Part B will be made based on DMC recommendation when Part A data is available and benefit risk ratio will be evaluated.

## 4.2 SCIENTIFIC RATIONALE FOR STUDY DESIGN

The participants enrolled in this study will be at an early stage of ALS to capture the effect of treatment on the disease course, especially because the mechanism of action of SR443820 modifies the disease pathology, rather than providing symptomatic alleviation. Participants who have a very slow ALS progression rate (<0.5 points/month in ALSFRS-R) prior to the screening visit will be excluded from the study to ensure that the study efficacy results will be interpretable. Part A of this study uses a randomized, double-blind, placebo-controlled design as it is the gold standard to demonstrate the efficacy and safety of SAR443820. Meanwhile, Part B of this study is an open-label extension during which both safety and efficacy data are collected to characterize the long-term treatment effects of SAR443820.

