**Statistical considerations:**

**Sample size determination:**

A sample size of 261 participants in total is needed to achieve an 80% power to detect a 30% reduction in SAR443820 compared with placebo in change of the Amyotrophic Lateral Sclerosis Functional Rating Scale Revised (ALSFRS-R) from baseline to Week 24, assuming a change of █ points from baseline in ALSFRS-R in the placebo arm with a standard deviation of █ points at Week 24, and a 20% drop-out rate. Sample size is estimated via simulation with a 2-sided 5% significance level.

**Primary endpoint in Part A:** The primary efficacy endpoint in Part A is the change from baseline in the ALSFRS-R total score to Week 24.

The **primary estimand** will be the difference (SAR443820 vs placebo) in the mean change from baseline in the ALSFRS-R score estimated in the intent-to-treat (ITT) population regardless of whether participants completed the treatment period. This estimand corresponds to a “treatment policy strategy” and will be using all available data and missing data will not be imputed.

The primary analysis will be based on the primary estimand, which includes data collected for the primary endpoint for all participants included in the ITT population.

A mixed-effect model with repeated measure (MMRM) model will be fitted to change from baseline in the ALSFRS-R score, which will include the fix effects of treatment (SAR443820 or placebo), visit (as a categorical variable), baseline ALSFRS-R score, baseline serum neurofilament light chain (NfL), randomization strata of the geographic region of the study site, ALS onset region (bulbar or other areas), use of riluzole (yes or no), use of edaravone (yes or no), use of the combination of sodium phenylbutyrate and taurursodiol (yes vs no), treatment-by-visit interaction, baseline NfL-by-visit interaction and baseline ALSFRS-R score-by-visit interaction. The least squares mean difference in the ALSFRS-R change from baseline at Week 24 between SAR443820 and placebo, together with the p-value and the 95% confidence interval (CI) for the difference, will be estimated from the MMRM model.

Subgroup analysis will be specified in the SAP.

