3.2.2 Main analytical approach

Part A

The primary endpoint in Part A will be analyzed with the estimand defined according to the following attributes:

- Endpoint: Change from baseline in the ALSFRS-R total score to Week 24
- Treatment condition: SAR443820 will be compared to placebo
- Analysis population: ITT population
- Intercurrent events (IE):
 - The IMP discontinuation IE will be handled with the treatment policy strategy; The primary endpoint will be assessed based on all assessments irrespective of the IMP discontinuation
- Population-level summary: The primary endpoint will be analyzed using MMRM with change from baseline in ALSFRS-R total score up to Week 24 as response variable, and treatment, visit, randomization strata of the geographic region of the study site, ALS onset region (bulbar or other areas), use of riluzole (yes or no), use of edaravone (yes or no), use of the combination of sodium phenylbutyrate and taurursodiol (yes or no), treatment-by-visit interaction, disease duration (from first symptom onset to the screening visit), baseline ALSFRS-R score, baseline NfL, disease duration-by-visit interaction, baseline NfL-by-visit interaction and baseline ALSFRS-R score-by-visit interaction as covariates. If less than 10 participants in a randomization strata level, then the corresponding factor will not be included as a covariate in the MMRM model.

The least squares mean difference in the ALSFRS-R change from baseline at Week 24 between SAR443820 vs placebo, together with the p-value and the 95% CI for the difference, will be estimated from the MMRM model using weights for each stratum equal to the overall proportion of participants in each stratum (ie, “population weight”) by inclusion of the OBSMARGINS option in the LSMEANS statement. Plots of least squares means (\pm standard error) over time will be provided.

This model will be implemented using the SAS MIXED procedure with an unstructured covariance matrix to model the within-participant errors. Parameters will be estimated using the restricted maximum likelihood method. The denominator degrees of freedom will be estimated using the Kenward-Roger approximation. This model will provide baseline adjusted least-squares means estimates at Week 24 for SAR443820 and placebo, together with their corresponding standard errors and CIs. If this model fails to converge, the following variance-covariance structures will be tested in this order:

- Heterogeneous Toeplitz
- Heterogeneous AR(1)

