3.4.3 Comparison with external control

A matched analysis using data from historical clinical trial database (for example, PROACT) as a control will be conducted to demonstrate the superiority of SAR443820 on slowing down disease progression and prolonging survival over 104 weeks of treatment period.

Matching procedure

1. Pre-matching filtering: The participants in the historical clinical trial database will be filtered by the following factors that match our trial eligibility criteria and duration:
 - Age 18 – 80 years, inclusive
 - First ALS symptom onset ≤ 2 years
 - Baseline SVC (%) $\geq 60\%$
 - Baseline ALSFRS-R decline rate $\geq 0.5/\text{month}$
2. Propensity score matching: Propensity score matching seeks to balance the distributions of known prognostic covariates in treatment and control group to resemble what would occur had the treatment been randomly assigned. A logistic regression for the treatment group as the dependent variable is performed to obtain the propensity score with the abovementioned matching variables, using all the participants (planned for 174) randomized to the SAR443820 arm and the participants from the historical clinical trial database after filtering as described above. Each participant in the SAR443820 treated group will be matched 1:1 using the Mahalanobis distance to a participant in the historical clinical trial database. Matching will be performed with replacement.

To assess the success of the matching procedure, summary statistics of baseline matching variables will be presented and compared between the two treatment groups before and after matching to assess post-match balance.

Post-matching statistical analysis

Once the matching is performed, the comparison between participants who were randomized to SAR443820 and placebo arm generated from the historical trial database will be provided for the following endpoints using the similar analyses models as described for the primary and secondary endpoints in [Section 3.2.2](#) and [Section 3.3.1.2](#).

- Combined assessment of function and survival (CAFS) score at Week 52, Week 76, and Week 104
- Change from baseline in ALSFRS-R total score to Week 52, Week 76, and Week 104
- Time from baseline to the occurrence of either death or permanent assisted ventilation (>22 hour daily for >7 consecutive days) whichever comes first
- Time from baseline to the occurrence of death

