4 SAMPLE SIZE DETERMINATION

The proposed sample size ($n = 261$) provides an approximately 80% power to detect a 30% reduction in SAR443820 compared with placebo in the change of ALSFRS-R from baseline at Week 24, assuming a change of █ points from baseline in ALSFRS-R in the placebo arm with a standard deviation of █ points, and a 20% drop-out rate. Sample size is estimated via simulation with a 2-sided 5% significance level.

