5.3 APPENDIX 3 DEMOGRAPHICS AND BASELINE CHARACTERISTICS, PRIOR OR CONCOMITANT MEDICATIONS

Demographics, baseline characteristics, medical surgical history

The following demographics and baseline characteristics, smoking and alcohol history, medical and surgical history and disease characteristics at baseline will be summarized using descriptive statistics in the randomized population.

Demographic and baseline characteristics include:

- age in years as quantitative variable and in categories (< 65, \geq 65)
- gender (Male, Female)
- race (White, Black or African American, Asian, American Indian or Alaska Native, Native Hawaiian or Other Pacific Islander, Multiple, Unknown, Not reported)
- ethnicity (Hispanic or Latino, not Hispanic or Latino, Unknown, Not reported)
- region (US, non-US; North America, Europe, Asia)
- weight in kg as a quantitative variable
- BMI in kg/m² as a quantitative variable and in categories (< 25, \geq 25 to $<$ 30, \geq 30)

Smoking and alcohol habits:

- smoking history (Never, Current, Former)
- cessation prior to screening for Former smokers in months
- cigarettes per day for smokers
- frequency of alcohol drinking in the past 12 months (Never, Occasional, At least monthly, At least weekly, At least daily)
- Number of standard alcohol drinks on typical day when drinking (1 or 2, >2)

Disease characteristics at baseline include:

- ALS diagnosis type (possible, clinically probable ALS, clinically probable laboratory-supported, or clinically definite)
- initial disease onset location (bulbar, other)
- ALS disease duration (years) from first symptom onset to the screening visit
- time since diagnosis (years)
- ALSFRS-R total score
- ALSFRS-R pre-study slope defined as (48-ALSFRS-R score at the screening visit)/duration in months between the screening visit and disease onset)
- SVC

- use of Riluzole collected from IRT
- use of Edaravone collected from IRT
- use of the combination of sodium phenylbutyrate and taurursodiol collected from IRT
- use of Riluzole and Edaravone collected from IRT
- use of Riluzole and the combination of sodium phenylbutyrate and taurursodiol collected from IRT
- use of Edaravone and the combination of sodium phenylbutyrate and taurursodiol collected from IRT
- use of Edaravone and the combination of sodium phenylbutyrate and taurursodiol collected from IRT

Baseline safety and efficacy parameters (apart from those listed above) will be presented along with the safety and efficacy summaries.

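### Adding the prestudy ALSFRS-R slope to the primary MMRM would be a cheap, modest gain in precision; leaving it out is not an error

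*Protocol*

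**What the plan says.** - **Selection.** Criterion I 04 requires a prestudy slope of at least 0.5 points/month, computed as 48 minus the screening score, divided by months since onset. Protocol 4.2 gives interpretability of the efficacy results as the reason: "Participants who have a very slow ALS progression rate (<0.5 points/month in ALSFRS-R) prior to the screening visit will be excluded from the study". I 03 caps disease duration at 2 years and sets no lower limit.
- **Tabulation.** SAP Appendix 3 (5.3) lists among the baseline disease characteristics the "ALSFRS-R pre-study slope defined as (48-ALSFRS-R score at the screening visit)/duration in months between the screening visit and disease onset".
- **Matching.** SAP 3.4.3 filters the historical controls on age, time since onset, SVC and ALSFRS-R decline rate. It then builds the propensity score from those same variables and says: "Propensity score matching seeks to balance the distributions of known prognostic covariates in treatment and control group".
- **Primary model.** Besides treatment, visit, their interaction and the randomisation strata, SAP 3.2.2 and Table 2 include "disease duration (from first symptom onset to the screening visit), baseline ALSFRS-R score, baseline NfL, disease duration-by-visit interaction", with by-visit terms for NfL and baseline score as well. There is no slope term and no score-by-duration term, and no reason is given.
- **Sizing.** The trial of 261 "provides an approximately 80% power to detect a 30% reduction in SAR443820 compared with placebo" in the Week 24 change, with 2:1 allocation and 20% dropout. The placebo decline and its SD are redacted.

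**The concern.** The model holds the two ingredients of the slope, score and duration, as separate linear terms. A ratio is not a linear combination of its parts. For a loss of 8 points, the slope is 8/16 = 0.5 per month at 16 months, 8/8 = 1.0 at 8 months and 8/4 = 2.0 at 4 months. A linear duration term gives every month the same weight, so it fits least well for people with short duration and fast decline.

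If the slope predicts the Week 24 change beyond score, duration and NfL, that part stays in the residual and widens the confidence interval of the one test that declares the study positive. That test also gates the five secondary endpoints in SAP 3.5, and planned power is only about 80%. The covariate is known at baseline and complete by eligibility.

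**Working it through.** **1. The plan's own figure.** Stated: 261 participants (174 and 87), 80% power, 2-sided 5%, 20% dropout; "Sample size is estimated via simulation with a 2-sided 5% significance level". With the decline and SD redacted, 261 cannot be reproduced independently. It can only be inverted with the two-means normal formula:

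delta/SD = (1.96 + 0.8416) × √(1/n_placebo + 1/n_active)

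- Dropouts lost: 261 × 0.8 = 208.8 evaluable, i.e. 69.6 and 139.2. delta/SD = 2.8016 × √(1/69.6 + 1/139.2) = 2.8016 × 0.1468 = 0.411. With delta equal to 30% of the placebo decline, SD = 0.30/0.411 = 0.73 of that decline.
- Dropouts counted in full (87 and 174): delta/SD = 0.368 and SD = 0.82 of the decline.

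Rounding up gives 70 placebo and 210 evaluable, and 210/0.8 = 263 after rounding up. This is consistent with 261 but circular. The documents do not say whether the SD is raw or covariate-adjusted, so taking 80% as the power of the planned model is itself an assumption.

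**2. How much of the slope the model already holds.** Six eligible populations were simulated under I 03 and I 04:

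- median slope 0.6, 0.8 or 0.9 points/month with log-scale SD 0.5 or 0.7, and a minimum score of 20 or 30;
- duration at most 24 months and slope at least 0.5;
- Day 1 score up to 4 weeks after screening, with 1-point noise.

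Linear terms in score and duration explained 78 to 84% of the variance of slope. Other assumed populations gave values between 74% and 92%.

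**3. What adding slope buys.** The documents give no slope-outcome correlation. The assumption here is that slope alone explains 5 to 30% of the variance of the Week 24 change, with NfL either uninformative or correlated 0.4 with log slope. With r the ratio of residual variance with slope to that without:

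power = Φ(2.8016/√r − 1.96); equivalent N = 261 × r

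| Slope alone explains | r | Power from 80% | Equivalent N |
|---|---|---|---|
| 5% | 0.989–0.992 | 80.3–80.5% | 258–259 |
| 10% | 0.976–0.983 | 80.7–80.9% | 255–257 |
| 20% | 0.948–0.962 | 81.5–82.1% | 247–251 |
| 30% | 0.915–0.938 | 82.5–83.4% | 239–245 |

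At the top end, 2.8016/√0.9148 − 1.96 = 0.969 and Φ(0.969) = 83.4%; 261 × 0.9148 = 238.8, about 22 fewer participants. NfL changed these figures little.

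**4. Sensitivity.** A wider grid of 288 settings varied:

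- minimum duration (2 or 5 months) and log-slope SD (0.5 to 0.7);
- correlation of prestudy with on-study slope (0.4 to 0.7) and of NfL with on-study speed (0 or 0.6);
- Week 24 noise SD (2 to 4 points), the score floor, and decline between screening and Day 1.

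The largest reduction in residual variance was 6.8% (power 82.7%). At a slope correlation of 0.55 it was 0 to 3.2% (80.0 to 81.2%), and many settings were under 1%. All figures use a normal approximation, count dropouts as lost and give no credit for partial MMRM data.

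**The case against.** The strongest reply is that nothing here is wrong. The model is prespecified and already adjusts for score, duration and NfL by visit. Disease duration was added in SAP version 1 on clinical input, so the sponsor considered how to adjust. The SAP also notes that fast progressors have higher NfL, so the model already holds a marker of progression rate. A fourth, overlapping covariate is then a matter of preference. All of this stands, and it is why the gain is small.

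A reader might infer that the SAP itself declares slope prognostic for Part A. It does not. The phrase about prognostic covariates in SAP 3.4.3 is a general description of propensity matching. Decline rate enters by reference to a filter list that mirrors eligibility, and the setting is a non-randomised comparison in which confounding must be handled. Protocol 4.2 is likewise an enrichment rule and says nothing about covariates.

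Two practical objections also stand. The text under SAP 3.2.3 is not visible, and SAP 3.3.1.3 refers to it for a rank ANCOVA of CAFS on prognostic factors; slope may be used there, though that would not alter the primary MMRM. And because I 03 has no lower limit on duration, a raw ratio entered linearly could give high leverage to very short durations, so the form of the covariate needs thought.

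**Conclusion.** This is an inexpensive improvement, not an error. The slope is selected on, tabulated and matched on, but it is absent from the primary model, and two additive terms do not reproduce it. Randomisation means the omission does not confound the treatment comparison; only precision is affected.

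Under the assumptions above, adding slope removes about 0 to 8% of the Week 24 residual variance (8.5% in the single most favourable setting). From 80% that is roughly 0 to 3 power points, and at or below about 2 unless slope alone explains more than roughly 20% of the outcome variance. It never lowered power in the settings run.

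A reader might infer a material loss of power. Favourable simulation settings can yield a 16.5% reduction in residual variance, which would mean Φ(2.8016/√0.835 − 1.96) = 86.6% power, worth 261/0.835 − 261 = 52 participants. The documents do not support that. The SD and placebo decline are redacted, no slope-outcome correlation is given, and the calculations in steps 3 and 4 reach about half that reduction at most.

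**What to change.** Before the Part A database lock:

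1. In SAP 3.2.2 and Table 2, add the I 04 prestudy slope and its by-visit interaction to the primary MMRM, keeping baseline ALSFRS-R, disease duration and NfL.
2. Prespecify the form. A log transform is natural: log slope = log(48 − score) − log(months). I 04 keeps the slope at 0.5 or above, so the log always exists, and equal ratios become equal steps, which limits the leverage of very short durations. Another stated rule for short durations would also serve.
3. Carry the term into the subgroup interaction model (SAP 3.2.5).
4. Align the model text in Protocol 9.4.2 and the synopsis. That text does not list disease duration either, so it already differs from the SAP.

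The cost is an SAP revision with matching protocol text, and one partly collinear covariate using about one degree of freedom per visit in a trial of 261. No new data are needed. If the sponsor prefers to keep the current model, a prespecified sensitivity analysis with slope, or a sentence on why score, duration and NfL suffice, would answer the point. Timing matters: the same change made after unblinding would look data-driven.
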